5.3 Analysis Variables

5.3.1 Subject's Disposition and Analysis Sets

Disposition will be summarized descriptively using counts and percentages for Enrolled Population by treatment sequence, and for the ITT Population by planned treatment.

The number and percentage of subjects screened, screen failures, entered the study, randomized, and completed the study will be presented, together with number and percentage of subjects who prematurely discontinued from the study along with reasons for study discontinuation by treatment sequence and overall.

A listing of the subject's disposition status will be provided. The number of subjects in each analysis set will be summarized descriptively by treatment with counts and percentages. A listing of subject's inclusion to analysis sets will be provided. A subject's eligibility with inclusion/exclusion criteria completions or deviations will be listed.

5.3.2 Demographics and Baseline Characteristics

Demographic data will include gender (male, female), age, age group (≥ 18 to < 65 and ≥ 65 years), race, ethnic origin and treatment group.

Baseline characteristics will include:

- body weight, height, BMI;
- Gold Scale of Hypoglycemia Unawareness;
- average correction factor per unit of insulin (mg/dL);
- duration of Type 1 diabetes calculated in years.

Subjects who:

- were diagnosed with Type 1 diabetes by a health care practitioner;
- were taking daily insulin treatment;
- has assigned correction for managing their hypoglycemia, and average correction factor per unit of insulin (mg/dL) for subjects with assigned correction factor.

Demographics and baseline characteristics will be summarized for all subjects overall and by treatment. Summary statistics (e.g., number of subjects, mean and standard deviation, median and range) will be generated for all continuous variables (i.e., age and weight,) and the number and percentage of subjects within each category will be presented for all categorical variables (i.e., gender, race, ethnicity,). The summary results will be based on the ITT population.

5.3.3 Medical History

Medical history will consist of two parts:

- 1) **General Medical History.** This data will be coded using the Medical Dictionary for Regulatory Activities (MedDRA, latest version), listed and summarized with descriptive statistics by System Organ Class (SOC) and Preferred Term (PT).
- 2) **Diabetes History** will include information about date of diagnosis of Type 1 Diabetes diagnosis, current daily insulin treatment and correction factor for managing hypoglycemia. This data will be listed separately as part of demographics and baseline characteristics.

Duration of T1D in years will be calculated using date of informed consent and date of diagnosis as integer part of

$$[\langle \text{Date of Informed Consent} \rangle - \langle \text{Date of Diagnosis} \rangle + 1] / 365.25.$$

If day of diagnosis is unknown, then day will be imputed as '01' (first day of the month).

If month of diagnosis is unknown, then month will be imputed as '01' (Jan of year of diagnosis).

Duration of T1D will be listed and analyzed with descriptive statistics as Baseline characteristics.

5.3.4 Pregnancy and Childbearing Potential

For female subjects, pregnancy test and/or childbearing potential will be listed.

5.3.5 Prior and Concomitant Medications

Medications will be coded with the latest version of the WHO drug dictionary, listed and presented by ATC Class 2 and Preferred Term.

If a medication cannot be coded by WHO dictionary, it will be coded as "WHO Code Not Defined".

Each medication will be classified as prior, concomitant, or both.

Any medication taken within 4 weeks before Day 1 will be considered as prior.

Any medication taken on or after the drug administration (Day 1) will be considered as concomitant.

In case when start/stop date is incomplete, or medication is ongoing, the following assumption will be made for Prior/Concomitant classification:

- If there is reasonable possibility that medication was taken within 4 weeks (28 days) before study drug administration, the medication will be considered as prior;
- If there is no evidence that medication was taken before the drug administration, medication will not be classified as prior;
- If there is reasonable possibility that medication was taken on or after study drug administration and there is no evidence that medication intake was stopped before first drug administration, then the medication will be classified as concomitant.

If dates of medications are incomplete, missing, or medication is ongoing, the medication will be considered as concomitant if there is no evidence that the medication intake stopped before study treatment. The medication will be considered as prior if there is an evidence that medication intake started before the study treatment, and there is a possibility that medication intake started not earlier than 6 months before screening.

Prior and Concomitant medication will be summarized and listed with ATC Class 2 and preferred term (PT) by treatment sequence and overall for the Safety population.

Concomitant medication which started or changed with dosing/regimen after study drug administration, will be attributed to Treatment Period 1 or 2 by start date and analyzed descriptively by treatment received for the Safety population.

Patients may have more than one medication per ATC category and PT. At each level of patient summarization, a patient will be counted only once.

5.3.6 Efficacy Variables

The following efficacy variables will be utilized in the efficacy analyses.

5.3.6.1 Primary Endpoint

Positive Plasma Glucose Response 1 (PGR1)

Positive Plasma Glucose Response 1 (PGR1) is defined as reaching a plasma glucose concentration ≥ 70 mg/dL (≥ 3.88 mmol/L) within 30 minutes of study drug injection (actual time). (The baseline plasma glucose is the blood glucose reading immediately before study drug dosing.)

Positive Plasma Glucose Response 2 (PGR2)

Positive Plasma Glucose Response 2 (PGR2) is defined as reaching an increase in plasma glucose concentration ≥ 20 mg/dL (≥ 1.11 mmol/L) within 30 minutes of study drug injection (actual time).

Positive Plasma Glucose Response (PGR)

For the primary endpoint, Positive Plasma Glucose Response (PGR) is defined as reaching Positive Plasma Glucose Response 1 (PGR1) **or** Positive Plasma Glucose Response 2 (PGR2).

For the primary endpoint, treatment groups will be compared for rates of achieving a positive plasma glucose response. The comparison will be performed using Intention to Treat (ITT), Modified Intent-to-Treat (mITT) and the Per-Protocol (PP) populations. Risk difference in rates of failing to achieve Positive Plasma Glucose Response (PGR) will be assessed for G-Pen versus GlucaGen Hypokit used as reference and the associated 95% CIs presented.

5.3.6.2 Secondary Endpoints

5.3.6.2.1 Pharmacodynamic (PD) Parameters

The PD endpoints will be derived from the individual glucose profiles. Pharmacodynamic characteristics, including:

- AUC_{0-90} and AUC_{0-180} : plasma glucose area under the concentration versus time curve for 90 and 180 mins from glucagon administration;
- C_{max} : Maximum concentration of glucose in plasma;
- T_{max} : time (in mins) when Glucose C_{max} is reached;

The following rules will be used for incomplete data:

- AUC: If there are missing data points before the last observed value, they will be extrapolated using the last two data points;
- AUC: If there are missing data points after the last observed value, they will not be imputed, and the AUC will be treated as not defined;
- If insulin starts after receiving glucagon, the glucose values post insulin start will be censored out and considered as missing. This is also considered a major protocol deviation.

Comparison between the treatments will be performed using a mixed model with treatment, period and treatment*period as fixed factors and subject as a random factor.

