5. Subcutaneous administration of the study drug will be made to the abdomen around the umbilicus as per [Section 9.3.3](#). Clock time of study drug administration will be recorded in the source documents. After study drug injection, the study product will be disposed in a location away from the subject in a manner that maintains the blind. After disposal, the blindfold and headphones will be removed from the subject.
6. Following study drug administration, plasma glucose will be measured every 5 ± 2 minutes through 90 minutes, and every 30 ± 2 minutes thereafter through 180 minutes post-dosing.

7. At 180 minutes post-dosing, the subject will resume insulin therapy and be given a meal as per the standard practice at each site. The subject can be discharged from the clinic if their plasma glucose is >100 mg/dL (> 5.55 mmol/L) and the subject is deemed medically stable.
8. After study drug administration and before 180 minutes post-dosing, if rising glucose levels are observed and if deemed medically necessary, insulin therapy or other medical intervention may be initiated by the Investigator.
 - a. Such intervention is not recommended to occur before 90 minutes post-dosing of study drug.
 - b. Plasma glucose data and assessments of neuroglycopenic symptoms will be censored after the time of intervention, per the statistical analysis plan.
 - c. These interventions (such as insulin, carbohydrates, or a meal) prior to 180 minutes post study drug administration should be captured in the source documents, and further glucose measurements may be performed at the discretion of the Investigator.

Hypoglycemia Symptom Assessments

Subjects will complete a questionnaire regarding severity of hypoglycemia symptoms ([Appendix 1](#)) at the following time points:

1. Just before the IV bolus push dose of insulin is given at the start of the hypoglycemia induction procedure (baseline),
2. Every time blood is drawn for evaluation of plasma glucose concentration during the induction procedure,
3. Just before study drug is administered,
4. Every 5 ± 2 minutes after glucagon is administered until 90 minutes post-dosing, and every 30 minutes (coinciding with plasma glucose measurements) between 90 and 180 minutes post study drug administration.

Local Tolerability and Adverse Events

Local tolerability and AEs will be assessed as follows:

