3.3.2 Secondary Endpoints

For the secondary endpoints, treatment groups will be compared based on each of the following:

1. Rate of achieving a plasma glucose concentration > 70 mg/dL (> 3.88 mmol/L) within 30 minutes from injection of study drug.
2. Rate of achieving an increase in plasma glucose concentration > 20 mg/dL (> 1.11 mmol/L) within 30 minutes from injection of study drug.
3. Rates of positive symptomatic response, defined as relief of neuroglycopenic symptoms within 30 minutes from a decision to dose.
4. Rates of positive treatment response, defined as exhibiting either a positive plasma glucose response (within 30 minutes from injection of study drug) *or* a positive symptomatic response (within 30 minutes from a decision to dose).
5. Time to a positive plasma glucose response from injection of study drug.
6. Time to administer study drug from a decision to dose.

7. Pharmacodynamic (PD) characteristics of mean plasma glucose concentration (0 to 90 minutes post-dose), maximum observed concentration (C_{max}), time to maximum observed concentration (T_{max}), area under the concentration versus time curve from time 0 to 90 minutes (AUC_{0-90}), and area under the concentration versus time curve from time 0 to 180 minutes (AUC_{0-180}).
8. Time to (a) initial relief and (b) complete resolution of autonomic and neuroglycopenic symptoms of hypoglycemia from a decision to dose.
9. Time to resolution of the overall feeling of hypoglycemia from a decision to dose.
10. Safety endpoints, including adverse event (AE)/serious adverse event (SAE) rates, and changes in vital signs, laboratory variables, and physical exam/electrocardiogram (ECG) findings.
11. Tolerability endpoints, including: Draize scale scores for injection site erythema and edema as assessed by the investigator, and injection site discomfort and duration as assessed by subject questionnaire responses.

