6.4 General guideline for define the protocol time

Protocol time is needed to find the 30-minute glucose value as well as to generate most of the glucose or hypoglycemia score curves.

Protocol time will be developed based on the following procedures:

- Protocol time zero will be based on either receiving glucagon or decision to dose:
 - Receiving glucagon: T0 = actual time stamp of glucagon injection
 - Decision to dose: T0 = actual time stamp when dose decision is made

- Subsequent protocol times are calculated by the following minutes plus T0 (receiving glucagon):
 - 5, 10,15,20,25,30,35,40,45,50,55,60,65,70,75,80,85,90;
 - 120,150, and180.
- For any continuous (number) variable, the value at the protocol time will be determined by linear interpolation between the two adjacent time points.
- For any categorical (text) variable, the value at the protocol time will be determined using the nearest value:
 - Protocol time 5 – 85: -2 minute to +3 minute;
 - Protocol time 90: -2 minute to 15 minute;
 - Protocol time 120, 150, 180: -15 minute to +15 minute;
 - If multiple values are attributed to a single protocol time, then the last value will be used.

Several analyses will be conducted using both the protocol time based on study drug administration and the one based on decision to dose. These analyses will be noted in each of the corresponding sections.

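### For AUC, the SAP extrapolates interior missing glucose values although a later reading exists; linear interpolation would be more accurate and would remove an ambiguity

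*SAP*

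**What the plan says.** SAP 5.3.6.2.1 gives two rules for incomplete glucose data, both labelled as AUC rules. The first covers gaps inside the profile, that is, points missing before the last observed value: "they will be extrapolated using the last two data points". The second covers points missing after the last observed value: "they will not be imputed, and the AUC will be treated as not defined".

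SAP 6.4 sets a general method for continuous variables at protocol times: "the value at the protocol time will be determined by linear interpolation between the two adjacent time points". It states its purpose as follows: "Protocol time is needed to find the 30-minute glucose value as well as to generate most of the glucose or hypoglycemia score curves". AUC is not named there.

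The sampling grid is in Protocol 10.2.1.2, under preparation and administration of study drug: "plasma glucose will be measured every 5 ± 2 minutes through 90 minutes, and every 30 ± 2 minutes thereafter through 180 minutes post-dosing".

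AUC0-90 and AUC0-180 are listed secondary endpoints (SAP 3.3.2). SAP 6.6.2 compares the PD parameters by mixed model with 95% confidence limits, and SAP Appendix 1 plans a non-inferiority table for each AUC (14.2.2.2.3 and 14.2.2.2.4). The SAP does not state the integration rule for AUC, or whether nominal or actual times are used for it.

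**The concern.** Because trailing gaps are left alone, the first rule can apply only to a gap that has a reading on its far side. Extrapolation is the tool for the case where no later reading exists. Used here, it replaces a value bracketed by two readings with one projected from one side, and noise in the two source readings is amplified. The amplification is largest where the spacing changes from 5 to 30 minutes, because a slope estimated over 5 minutes is then carried forward over 30.

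The wording also leaves open which two points are meant. They could be the two just before the gap, or the final two of the whole profile extended backwards. Two programmers could follow the sentence and obtain different AUCs.

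Finally, the mean glucose curves are built by interpolation under SAP 6.4 while the AUC uses another method, and no text explains the difference. At stake are the accuracy and reproducibility of two secondary PD endpoints.

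**Working it through.** The plan gives no figure to reproduce. The grid comes from Protocol 10.2.1.2. The reading SD, the glucose profile and the linear trapezoid are assumptions.

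**Noise multiplier, 120-minute reading missing, 150-minute reading present**

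- Forward extrapolation from 85 and 90 minutes: y90 + (30/5)(y90 − y85) = 7·y90 − 6·y85. Multiplier √(49 + 36) = 9.2.
- Interpolation between 90 and 150 minutes: (y90 + y150)/2. Multiplier √(1/4 + 1/4) = 0.71.

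These multipliers depend only on the grid and on independent reading errors.

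**Error against the reading that would have been taken** (adds that reading's own variance)

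- Extrapolation: √86 = 9.27 times the SD, so 9.3 mg/dL at SD 1 and 27.8 mg/dL at SD 3.
- Interpolation: √1.5 = 1.22 times the SD, so 1.2 mg/dL at SD 1 and 3.7 mg/dL at SD 3.

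**Effect on AUC0-180.** The 120-minute point has trapezoid weight (150 − 90)/2 = 30 minutes. Take AUC0-180 near 28,000 min·mg/dL.

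- Extrapolation: 9.3 × 30 = 279, or 1.0%, at SD 1; 27.8 × 30 = 834, or 3.0%, at SD 3.
- Interpolation: 1.2 × 30 = 36, or 0.1%, at SD 1; 3.7 × 30 = 111, or 0.4%, at SD 3.

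**One 5-minute point missing.** Extrapolation is 2·y(−1) − y(−2), where y(−1) and y(−2) are the readings 5 and 10 minutes before the gap. The error multiplier is √(4 + 1 + 1) = 2.45, so 7.3 mg/dL at SD 3, against 3.7 for interpolation. With a weight of 5 minutes this is about 37 min·mg/dL, or 0.13% of AUC0-180.

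**Check on two assumed profiles**

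- Profile A: logistic rise from 48 mg/dL to about 198, falling by 0.4 mg/dL per minute after 90 minutes. AUC0-90 is 12,298 and AUC0-180 is 28,630.
- Profile B: gamma-shaped from 48 mg/dL to 208 at 75 minutes. AUC0-90 is 13,857 and AUC0-180 is 27,634.

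The table gives the noise-free error. Where an SD is shown, it comes from 3,000 runs with reading SD 3.

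| Missing | Forward extrapolation | Interpolation |
|---|---|---|
| One point at 15, 30 or 45 min (size, % of AUC0-90) | 0.02 to 0.15 | 0.02 to 0.05 |
| Three consecutive 5-minute points (size, % of AUC0-90) | 0.3 to 0.9 | 0.0 to 0.3 |
| 120 min (% of AUC0-180) | +1.4 to +1.6, SD 2.9 to 3.0 | −0.1 to −0.3, SD 0.4 |
| 150 min (% of AUC0-180) | +0.1 to +0.6, SD 0.8 | 0.0 to +0.3, SD 0.4 |
| 120 and 150 min (% of AUC0-180) | about +5, SD 8.5 to 8.8 | −0.15 to +0.05, SD 0.6 to 0.7 |

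**The other reading of the sentence.** If the final two points (150 and 180 minutes) are extended backwards, a missing 15-minute value in profile A becomes 230 mg/dL where the true value is 65. The shift is (230 − 65) × 5 = 825, and 825/12,298 = 6.7% of AUC0-90. Across both profiles, one missing point at 15, 30 or 45 minutes shifts AUC0-90 by 2.4% to 7.0%.

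**Equivalence.** Under a linear trapezoid, interpolating an interior point gives the same AUC as omitting it. With the 45-minute point removed from profile B, both routes give 27,628.3.

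**The case against.** The strongest reply is that the sentence is specific to AUC, seldom bites, and may be loose wording for interpolation. Several parts of that stand.

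- **SAP 6.4.** A reader might infer that the two sections contradict each other. The documents do not go that far. SAP 6.4 is stated for the 30-minute value and most of the curves, and SAP 6.6.2 applies protocol time to the mean-curve figures. Neither place applies it to AUC. The methods are inconsistent, but they do not clash over one quantity.
- **Cmax and Tmax.** A reader might infer that an extrapolated value could become a false Cmax. The rule is labelled for AUC, no imputation rule is attached to Cmax or Tmax, and SAP 3.3.2 and Protocol 5.3.2 define Cmax as an observed maximum. The SAP 5.3.6.2.1 wording, "Maximum concentration of glucose in plasma", does not bring imputed values in. A false Cmax would need a programming choice that the SAP does not make.
- **Frequency.** The route to lost late readings that the documents describe is intervention before 180 minutes, after which values are censored. Those gaps are trailing, so AUC becomes undefined and the extrapolation rule never applies. An isolated 120-minute gap is possible, but the documents give no frequency for it.
- **Assumed noise.** No document gives a reading SD, and Protocol 11.2 records the average of two analyzer leads. The mg/dL figures scale directly with the assumed SD, hence the range of 1 to 3.
- **Inference.** Suppose 10% of profiles have the 120-minute gap, with error SD 3% and bias 1.5%, and the AUC coefficient of variation is 15%. The added variance is 0.10 × (3² + 1.5²) = 1.1, against 15² = 225, or about 0.5%. The treatment comparison would barely change.

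These points reduce the importance of the issue but do not defend the rule. Where it applies, the SAP still prescribes the less accurate method in unclear words. If interpolation was intended, the same edit is needed.

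**Conclusion.** The point holds for AUC0-90 and AUC0-180 only, as a low-priority improvement. As written, the rule applies only where a later reading exists, discards that reading, and does not say which two points it uses.

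The noise multipliers of about 9.2 against 0.71 for a missing 120-minute point follow from the sampling grid, given independent reading errors. The percentages rest on assumed profiles, an assumed reading SD of 1 to 3 mg/dL and a linear trapezoid:

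- about 1% to 3% of AUC0-180 for that gap, as an error SD for the affected profile;
- well under 1% for an isolated 5-minute gap;
- about 2% to 7% of AUC0-90 for one early gap if the final two points of the profile are meant.

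The primary endpoint is not affected, because the rule concerns AUC and the primary endpoint is a 30-minute response.

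**What to change.** Replace the first AUC rule in SAP 5.3.6.2.1 with: *For AUC, interior missing values will be linearly interpolated between the adjacent observed values at actual times.* This is equivalent to a linear trapezoid on the observed points, and it brings the AUC method into line with SAP 6.4. The rule for trailing gaps can stay as it is. As an optional safeguard, add that Cmax and Tmax use observed values only, which restates the endpoint definition.

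The cost is one SAP sentence. It needs no new data and does not touch the primary analysis.

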After 180 minutes posttreatment, subjects will resume insulin pump therapy, if applicable, and will be given a meal. Subject may be discharged after 180 minutes posttreatment if their plasma glucose is > 100 mg/dL (5.56 mmol/L) and if medically stable. At the Investigator’s discretion, subjects’ prescribed insulin regimen can be restarted, or the meal can be given sooner, but not earlier than 90 minutes post-glucagon treatment, to prevent hyperglycemia or rebound hypoglycemia.

After a wash-out period of 7 to 28 days, subjects will return to the CRC and the study procedures will be repeated with each subject crossed over to the other treatment. After study-related procedures are performed on each of the treatment days, subjects will be discharged. A Follow-Up Visit will be

XSGP-304 Clinical Protocol
G-Pen (glucagon injection)

	
conducted 2 to 7 days after administration of the final dose of study drug as a safety check.
 
Tolerability will be assessed by comparing AE reports between the G-Pen and GlucaGen Hypokit treatment groups. In addition, at the end of each treatment period the subjects will complete questionnaires to assess injection site discomfort, and the Investigator will use a modified Draize scale to evaluate the injection sites after each administration.

Data management and statistical analysis:	
Data will be entered into an electronic Case Report Form (eCRF) by the study site personnel. Data will be monitored at on-site visits by Xeris personnel or by a contract research organization (CRO) delegated by Xeris. A stand-alone Statistical Analysis Plan (SAP) will be written to detail all protocol specified analyses. The SAP will take precedence over the protocol. The primary endpoint will be analyzed using an exact test procedure based on the conditional distribution for a maximum clinically acceptable non-inferior margin of $\leq 5\%$.

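### AUC0-180 becomes undefined when insulin is started for rising glucose, so its missingness depends on the outcome it measures, and nothing in the analysis plan addresses this

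*SAP*

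**What the plan says.** **Deletion rule.** SAP 5.3.6.2.1 provides that, if insulin starts after glucagon, "the glucose values post insulin start will be censored out and considered as missing". For points missing after the last observed value, "they will not be imputed, and the AUC will be treated as not defined". The same section classes the insulin start as a major protocol deviation.

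**When insulin may start.** Protocol 10.2.1.2 (Preparation and Administration of Study Drug), reproduced in SAP 4.1, states that before 180 minutes, "if rising glucose levels are observed and if deemed medically necessary, insulin therapy or other medical intervention may be initiated by the Investigator". It adds: "Such intervention is not recommended to occur before 90 minutes post-dosing of study drug". The Synopsis lets the investigator restart the insulin regimen or bring the meal forward, "but not earlier than 90 minutes post-glucagon treatment, to prevent hyperglycemia or rebound hypoglycemia". No numeric trigger is given.

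**Sampling.** Glucose is read every 5 minutes to 90 minutes, then "every 30 ± 2 minutes thereafter through 180 minutes post-dosing".

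**Analysis.** SAP 6.6.2 compares PD parameters with a mixed model (treatment, period, their interaction, random subject) in the mITT population. It reports a difference p-value and a 95% interval labelled as a non-inferiority test. SAP 7.1 allows no further imputation. The only missing-data sensitivity analysis, in SAP 6.5, is for the primary endpoint.

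**Blinding.** Protocol 9.2 and SAP 4.4 blind the subject only.

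**The concern.** AUC0-180 is a named secondary endpoint with its own planned non-inferiority table (14.2.2.2.4). The event that deletes it is triggered by the glucose course that it summarises. A comparison of the AUCs that remain is not a comparison of the drugs in all treated subjects. The drug with more high or still-rising profiles tends to lose more of them, and the person who decides on insulin knows which drug was given.

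The same censoring shortens the profiles from which Cmax and Tmax are taken. The SAP has no undefined rule for these, so a peak cut off by insulin is reported as the peak.

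**Working it through.** **1. Rule chain.** An insulin start before 180 minutes makes later values missing. At least the 180-minute reading is lost, so a trailing point is missing and AUC0-180 is undefined. AUC0-90 is lost only if insulin starts before 90 minutes, which is not recommended.

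**2. Why the model does not repair this.** A random-subject model on one AUC per period is valid if missingness depends only on data in the model. Here it depends on glucose readings in the same period, which are not in the model. The subject's other-period AUC is only a partial substitute. The 19 readings from 0 to 90 minutes (0, 5, ..., 90) go unused.

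**3. The plan's own figures.** There are none to reproduce. No AUC0-180 effect, SD, intervention rate or margin is stated, so every input below is an assumption.

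**4. Direction, in SD units.** AUC is Y = u + e + δT, with T = 1 for G-Pen, Var(u) = ρ and Var(e) = 1 − ρ. The insulin trigger is L = cY + √(1 − c²)·z, with z standard normal. Y is undefined when L exceeds the cut-off that removes a fraction f. The crossover model was fitted by maximum likelihood to 200,000 simulated subjects per row. Attenuation is 1 − estimate/δ.

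Same trigger and spread for both drugs:

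| δ | ρ | f | c | Estimate | Attenuation |
|---|---|---|---|---|---|
| 0.30 | 0.5 | 10% | 0.9 | 0.247 | 18% |
| 0.30 | 0.5 | 20% | 0.9 | 0.217 | 28% |
| 0.30 | 0.5 | 40% | 0.9 | 0.178 | 41% |
| 0.30 | 0.5 | 20% | 0.5 | 0.274 | 9% |
| 0.30 | 0.5 | 20% | 0 | 0.305 | none |
| 0.30 | 0.2 | 20% | 0.9 | 0.200 | 33% |
| 0.30 | 0.8 | 20% | 0.9 | 0.255 | 15% |
| −0.30 | 0.5 | 20% | 0.9 | −0.216 | 28% |
| 0 | 0.5 | 20% | 0.9 | −0.003 | no bias |

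Trigger or spread differing by drug (ρ = 0.5, f = 20%, c = 0.9):

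| Assumption | Estimate, δ = 0.30 | Estimate, δ = 0 |
|---|---|---|
| Cut-off 0.3 SD higher after G-Pen | 0.309 | +0.094 |
| Cut-off 0.6 SD higher after G-Pen | 0.401 | not run |
| Cut-off 0.3 SD lower after G-Pen | not run | −0.095 |
| Cut-off 0.5 SD lower after G-Pen | 0.073 | not run |
| G-Pen SD 1.3 times reference | 0.031 | −0.184 |
| G-Pen SD 0.7 times reference | 0.397 | +0.175 |

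So a common trigger with similar spread shrinks the difference. A drug-dependent trigger or unequal spread can enlarge it, or create one where none exists.

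**5. Size, on the protocol sampling grid.** Assumed: rise of about 125 mg/dL, between- and within-subject SD 25 each, one drug 10% stronger, insulin when the 90-minute value is in the top fraction.

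| Periods intervened | True difference (mg/dL·min) | Planned analysis | Attenuation |
|---|---|---|---|
| 5% | 1644 | 1364 | 280/1644 = 17% |
| 10% | 1691 | 1288 | 403/1691 = 24% |
| 20% | 1650 | 1041 | 609/1650 = 37% |
| 30% | 1681 | 881 | 800/1681 = 48% |

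For scale, 1644/180 is about 9 mg/dL averaged over the period. A harder variant used noisy tails and a trigger combining slope and level with a random element for judgement. It gave about 9-67% attenuation at 5-30% intervened.

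**6. Does the remedy work?** In the noisy-tail variant, predicting the tail from the same profile's 0-90 minute readings recovered the true difference to within about 2%. In a case with drug-specific cut-offs, the true difference was 1767, the planned analysis gave 524, and prediction within drug gave 1770.

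**The case against.** A reader might infer that the drug difference is always biased toward zero because the strongest responses are removed. The documents support neither part.

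- **Direction.** Attenuation needs a similar trigger and spread for both drugs. An unblinded investigator using unquantified discretion guarantees neither. Even where attenuation occurs, it favours G-Pen only if GlucaGen is the stronger drug.
- **Who is removed.** Insulin requires rising glucose and medical necessity. A profile still rising after 90 minutes may be late rather than strong. The Synopsis also names rebound hypoglycemia as a reason for restarting insulin or giving an early meal. This objection stands against the word strongest, but it does not remove the bias. With δ = 0.30, ρ = 0.5 and c = 0.9, deleting the lowest 10% as well as the top 20% gave 0.148, an attenuation of 51%.

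The remedy can also be challenged. If simulated tails are fully determined by the earlier readings, recovery is automatic; that is why the noisy-tail result is the one relied on. An unstructured covariance over 22 times (19 plus 120, 150 and 180) has 22 × 23/2 = 253 parameters for 111 to 122 subjects, so a repeated-measures model needs a stated, simpler structure. Confining all Cmax and Tmax comparisons to 0-90 minutes would cap every late peak and should not be done.

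**Conclusion.** The defect is in the text and is worth correcting. Missingness of AUC0-180 depends on the outcome, the planned model does not use the readings that would explain it, and no sensitivity analysis covers it. The direction is conditional: attenuation under a similar trigger and spread, otherwise either way. There is no bias if the trigger is unrelated to AUC, or if the drugs are truly equal with the same trigger and spread.

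The range of roughly 10-65% rests on assumed profiles and intervention rates and is not an estimate for this trial.

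A reader might also infer a route to a false non-inferiority claim. The documents do not support that: they state no AUC margin, and the declared decision rests on the 30-minute response, which this rule leaves essentially untouched. AUC0-90 is largely spared.

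**What to change.** 1. **AUC0-180.** Replace the undefined rule with multiple imputation of the censored tail, within drug, from the same profile's observed readings. Equivalently, fit a repeated-measures model to glucose on the SAP 6.4 time grid, with a stated parsimonious covariance, and obtain AUC0-180 by trapezoid contrasts. State that the target is AUC0-180 without the intervention, which is what the censoring implies.
2. **Sensitivity.** Keep the complete-profile analysis in this role.
3. **Reporting.** Give, per drug, the number of profiles cut by insulin or other intervention and the reasons. Protocol 10.2.1.2 says "These interventions (such as insulin, carbohydrates, or a meal) prior to 180 minutes post study drug administration should be captured" in source documents; times and reasons must also reach the analysis data. Flag Cmax and Tmax values taken from cut profiles.
4. **Reconcile.** SAP 5.3.6.2.1 calls an insulin start a major protocol deviation, while Protocol 10.2.1.2 permits it. Under SAP 5.1.3 that label removes the subject from the PP population. The AUC rule names insulin only, whereas the protocol's censoring covers other interventions. SAP 4.1 says both that censoring runs from drug administration and, quoting the protocol, that it runs from the intervention.

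The cost is SAP wording and extra programming, with no new samples. The main assumption is that the tail is predictable from glucose already observed. This fits the stated trigger, but would fail to the extent that insulin is started for unrecorded reasons.
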